The aim of this study is to assess the effects of clinician racial bias on end-of-life communication and to develop interventions to reduce the effects of implicit bias on quality of clinician communication. There are two study objectives: (1) Establish which communication behaviors in the end-of-life setting are most affected by clinician implicit racial bias and explicit stereotyping. (2) Pilot a theory-driven intervention to improve clinician communication and reduce disparities in quality end-of-life care. These objectives will be met in two study phases.

Methods/Design:**Phase 1:****Methods:**

(1) I will develop a case depicting a hospitalized 72-year-old with lung cancer and sepsis due to pneumonia on high-flow nasal cannula with my mentorship team of experts in palliative medicine and critical care. I will design a clinical encounter with the caregiver to discuss goals of

Protocol #

care. 2) The caregiver encounter will be piloted with critical care and hospitalist physicians at Montefiore to ensure realism and achieve standardization.¹⁰⁸ Black standardized caregivers will be recruited from the pool of actors used by the Einstein Clinical Skills Center. (3) Standardized caregivers will be trained in the use of a communication assessment tool.¹⁰⁹ (4) 50 physicians will be recruited to participate in a videotaped high-fidelity simulation of the encounter. The session will be followed by a 1-hour communication skills training to allow participants to earn continuing medical education (CME) credit. (5) Immediately after the simulation subjects will complete the IAT and a questionnaire probing for attitudes about race and end-of-life care along with demographic questions. We will assess training needs by adapting a previously developed questionnaire measuring physicians' self-identified serious illness communication training needs by incorporating questions about bias mitigation skills.¹¹⁰ The IAT is publicly available here: <https://implicit.harvard.edu/implicit/selectatest.html>.

COVID-19 Concerns:

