Encounters will be videotaped. The amount of time the physician and standardized caregiver speak will be recorded. A five-point verbal communication rating scale will be used to rate physician (1) informativeness, (2) supportiveness, and (3) partnership-building and a modified version of the Nonverbal Accommodation Analysis System (NAAS).^{89,111} The NAAS will be modified to include physical distance and open/closed body language which were shown to be important in serious illness encounters.⁷³ Verbal communication will also be analyzed from transcripts of the videotaped encounters. Coded verbal communication will be categorized as data gathering, emotion talk, partnership building, biomedical topics and decision-making content. Videos and transcripts will be coded in the secure Dedoose™ qualitative data coding software. An extra passcode will be added for a second layer of data security.

Another questionnaire will be administered at the end of the training. We will ask physicians to rate their experiences with different educational modalities presented in the training session, such as feedback from observed encounters, communication drills and role-plays. Open-ended questions will be used to gather formative information that the researchers may not have considered. This questionnaire will be distributed at the end of the communication skills training.

Protocol #

Outcome measures:

The primary endpoint will be verbal dominance (ratio of clinician to patient speaking time with a ratio of >1 , meaning that the clinician dominated the discussion). Empirical evidence links this communication measure to implicit bias and to patient-centered communication outcomes.⁹⁹ Secondary endpoints will include duration of the communication encounter, verbal communication ratings, nonverbal communication behaviors coded with the NAAS and standardized caregiver ratings. Inter-rater reliability will be reported using Kappa values.

Analysis plan:

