Bivariate associations of communication scores with IAT scores will be estimated with Pearson or Spearman rank correlation coefficients depending on the distribution of the data. Generalized linear models (GLM) will be fit to the data to assess the associations of the IAT and racial attitudes with primary and secondary communication outcomes, while controlling for potential confounding variables including clinician age, gender and specialty. The identity link will be used in the GLM for continuous communication outcomes. Subgroup analysis will be performed in Asian, Black and Hispanic physicians if there are sufficient numbers in these groups to assess heterogeneity of the associations by race.

Power analysis:

The target sample size of 50 participants would have $>80\%$ power to detect a minimum correlation between IAT score and verbal dominance of $\rho \geq 0.38$ using a two-sided hypothesis test of a single correlation with a significance level of 0.05. This correlation is similar in magnitude to associations observed in prior studies; $B=11.0$ in one study and $r = 0.32$ in another.¹¹²

[figure not shown]
Protocol #

Phase 2:**Methods:**

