Initially, the mean change in verbal and nonverbal communication scores pre- and post-intervention will be evaluated within each intervention arm using paired *t*-tests or Wilcoxon tests if the data are not normally distributed. To assess whether communication scores improved more in the bias mitigation treatment compared with communication training only control, a generalized linear model will be fit to the data with post-intervention score as the outcome, and pre-intervention score and intervention arm as the main effects. In addition, we will investigate whether pre-intervention level of bias modifies the effect of bias mitigation training, e.g., those with more bias will have a greater difference in improvement between the intervention and control group, by including in the model an interaction term between IAT score and treatment group on communication scores. A positive interaction will indicate that implicit bias as measured by the IAT modifies the effect of treatment group on communication score. With 25 subjects per intervention arm, the study will have 80% power to detect an effect size of 0.8 between groups in pre-post change in communication scores with a two-sided Type 1 error rate of 5%. While this is considered a large effect size according to Cohen's criteria, we would like emphasize that this is a pilot study in which the primary goal is to assess feasibility and to generate preliminary data on the effect of the proposed communication training intervention for clinicians to mitigate the effects of implicit bias.

$\Delta y = \alpha + \beta_0(Tx) + \beta_1(IAT) + \beta_2(Tx \times IAT) + \epsilon_1$, where Δy = change in communication score, Tx = treatment group

Data Management/Analysis:

Protocol #

Communication behavior codes and data from the questionnaires and IAT stored on Montefiore's secure Box drive and will only be accessible by members of the research team. Video recordings will be stored on a password-protected hard drive accessible only to the research team.

Risks/Benefits:

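### The Phase 2 model and schedule ignore which actor plays the caregiver, although that actor's speaking time is the denominator of the primary endpoint

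*Combined protocol and SAP*

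**What the plan says.** All references are to the combined protocol and SAP.

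- **Caregivers (Phase 1, Methods).** "Black standardized caregivers will be recruited from the pool of actors". The plural is used; neither the number of actors nor an assignment rule is given. The encounter is to be piloted for realism and standardization.
- **Endpoint (Phase 1, Data collection and Outcome measures; Phase 2, Outcome measures).** "The amount of time the physician and standardized caregiver speak will be recorded". The endpoint text speaks of the patient's time, but the caregiver is the only other speaker who is timed, so the caregiver's speech is the denominator. Verbal dominance is primary in both phases.
- **Phase 2, Design.** Randomization is 1:1 in mixed blocks of 2, 4 and 6, with no stratification. Each clinician is recorded before and after training in one half-day workshop. Whether the actor is the same both times is not stated.
- **Phase 2, Analysis plan.** "a generalized linear model will be fit to the data with post-intervention score as the outcome", with pre-score and arm as main effects. The effect-modification model for change has treatment, IAT and their product. Neither has an actor term.
- **Phase 1, Analysis plan.** "Generalized linear models (GLM) will be fit to the data to assess the associations of the IAT and racial attitudes" and the communication outcomes, "while controlling for potential confounding variables including clinician age, gender and specialty". Power is for a "two-sided hypothesis test of a single correlation with a significance level of 0.05".

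**The concern.** In a ratio of speaking times, a talkative actor lowers every ratio he or she takes part in and a quiet one raises it. The actor is therefore built into the primary outcome. If actors differ, the Phase 2 model leaves that difference in the residual, and an uneven spread of actors over arms moves the estimated arm difference.

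Phase 2 is planned at about 80% power with no margin. One of its stated purposes is preliminary data on the training effect, so a noisier or shifted estimate would carry into the planning of later work. Identifying the actor in each encounter needs no new measurement.

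**Working it through.** **Inputs from the plan.** Phase 1: n = 50, correlation 0.38, two-sided 5%. Phase 2: 25 per arm, effect size 0.8, two-sided 5%, 80% power.

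**Assumed inputs (not in the documents).** Actor share of outcome variance v = 0 to 30%; number of actors k = 2 to 6; pre/post correlation 0.5 within actor.

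**Step 1: the plan's own figures.**
- Phase 2: the normal approximation gives 80.7% and the noncentral t with 48 df gives 79.1%. The stated 80% reproduces.
- Phase 1: Fisher z gives Φ(atanh(0.38)·√47 − 1.96) = 78.3%. A simulated t-test of r gives 79.1% and the fixed-x noncentral t 81.2%. The stated figure reproduces within 2 points.

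**Step 2: Phase 2 power with and without the actor term.** Set the variance of the post score to 1 and balance actors across arms. The residual variance of the ANCOVA is then:
- same actor pre and post: 1 − (0.5 + 0.5v)² without the actor term, and 0.75(1 − v) with it;
- unrelated actors: 1 − [0.5(1 − v)]² without it, and (1 − v) − 0.25(1 − v)² with it.

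Power is from the noncentral t with noncentrality 0.8·√12.5/√(residual variance), on 47 df without the term and 47 − (k − 1) with it. For k = 4:

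| v | Same actor: residual variance | Power | Unrelated actors: residual variance | Power |
|---|---|---|---|---|
| 10% | 0.698 → 0.675 | 91% → 92% | 0.798 → 0.698 | 87% → 91% |
| 20% | 0.640 → 0.600 | 93% → 95% | 0.840 → 0.640 | 86% → 93% |
| 30% | 0.578 → 0.525 | 95% → 97% | 0.878 → 0.578 | 84% → 95% |

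The unrounded gains are about 1 point with the same actor and about 4, 8 and 11 points with unrelated actors. They hardly change for k = 2 or 6. The starting power exceeds 79% because the pre-score is in the model. At v = 0 and k = 6 power goes from 89.2% to 89.1%.

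A simulation of the planned ANCOVA over 2 to 6 actors, comparing the plan with balancing plus adjustment, gave gains of about 1 to 3 points (same actor) and 3 to 14 points (not the same), and a cost of at most about 0.7 points at v = 0. The closed form lies within those ranges. Other readings of what 0.8 and 0.5 refer to move the figures by a few points.

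**Step 3: chance imbalance.** With post-encounter actors drawn at random, the arm difference due to actors has SD √(2v/25): 0.09, 0.13 and 0.15 outcome SDs at v = 10, 20 and 30%. Simulated 95th percentiles of its absolute size are about 0.18, 0.25 and 0.30, nearly the same for 2, 4 or 6 actors.

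**Step 4: type I error.** With random actor assignment and v = 20%, the simulated rate is 4.6% (2 actors) and 5.0% (4 actors). As an illustration only, ten arm-specific sessions of five clinicians with one actor each give about 8 to 17% at v = 10 to 30%.

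**Step 5: Phase 1.** Adjusted power is Φ(atanh(0.38/√(1 − v))·√(47 − (k − 1)) − 1.96), against 78.3% unadjusted. For k = 2 to 6 it is 77 to 74% at v = 0, 80 to 76% at 5%, 82 to 79% at 10% and 91 to 89% at 30%. Adjustment can therefore lose power when v is small and actors are many.

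**The case against.** The best counter-arguments are these.

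- **Standardization already limits actor differences.** Piloting is meant to do so and may succeed. But no check of actor speaking time is planned, and a goals-of-care conversation is interactive. The point stands as a reason not to assume a large variance share.
- **The pre-score absorbs the actor.** It does so in part if the same actor plays both encounters, which is why the gain is then only 1 to 3 points. The plan does not say that this will be so.
- **The gain depends on balance.** This is correct. In simulations with random, unbalanced actors, adjustment at 10% actor variance gained nothing material (78.8% against 79.3% with 4 actors; 79.6% against 79.1% with 6), and at 5% with 6 actors power fell from 78.8% to 76.8%. The scheduling rule and the model term belong together.
- **This is a pilot, and video allows actors to be identified later.** That lowers the stakes and makes a late repair possible, but a late repair cannot restore balance.

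A reader might infer that actors are in fact unbalanced across arms or change between encounters. The documents are silent on both, and silence is not evidence of either. A reader might also infer that Phase 1 excludes the actor. Its covariate list is introduced by the word including, so actor is unnamed, not ruled out.

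**Conclusion.** The point holds for Phase 2. An identifiable source of variation in the denominator of the primary endpoint is missing from an explicitly stated model, and no assignment rule controls it. Under random assignment the harm is lost precision and chance imbalance. That imbalance is already reflected in the standard error and must not be counted again as a bias.

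Two stronger readings are not supported. The first is that the planned test is invalid: type I error stays near 5% under random assignment, and the documents describe no arm-linked roster, which is what would be needed to bias the comparison. The second is that adjustment helps for any plausible number of actors: in Phase 1 it can cost a few points of power, and the bivariate correlation on which that phase is powered would be unchanged by adding a term to the GLM.

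The size rests on assumed variance shares of 10 to 30%, 2 to 6 actors and a pre/post correlation of 0.5. The documents supply none of these.

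**What to change.** For Phase 2:
- Record an actor study code for every encounter, and state how many actors will be used.
- Balance the post-encounter actors across arms, and apply the same pre/post pairing rule (same actor or different actor) in both arms.
- Add the post-encounter actor to the ANCOVA, as a fixed factor if there are few actors and otherwise as a random effect.

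For Phase 1, record the same code and prespecify a GLM with actor as a sensitivity analysis only, leaving the primary correlation as planned.

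The cost is a scheduling rule, a line of analysis text and one degree of freedom per extra actor. In Phase 2 this is under 1 point of power if actors do not differ at all.

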of group assignment. Block randomization will occur with randomly mixed block sizes of 2, 4, and 6. The allocator (research assistant) will hide block size from the executor (PI) in order to prevent the executor from predicting the next assignment. Randomization will be carried out by having a piece of paper that has the phrase “Intervention (Communication + Bias)” or “Control (Communication only)” placed inside an opaque envelope. The outside of the envelopes will be labeled with the sequence number. After a subject has been enrolled into the study and consented, the next sequence numbered envelope on the stack will be opened to determine the study group that the subject will enter.

Participants will be videotaped during high-fidelity simulations of encounters with caregivers described in phase 1, before and after receiving the intervention or control. The intervention and simulations will take place in one half-day workshop.

COVID-19 Concerns:

The Clinical Skills Center will be holding in-person simulations with standardized patients for the purposes of medical education starting in May 2021. The simulations in this study will not begin until after that time and will involve less risk than typical simulations because they will not entail a physical examination of the standardized caregiver. Actors and participants will be equipped with personal protective equipment including surgical masks. Trainers and participants in the training session will be required to wear provided surgical masks and remain six feet apart during the training sessions. If COVID-19 state or institutional guidelines prohibit these types of encounters at the time the simulations will be launched, the simulations and training will be adapted to a virtual format and nonverbal behavior coding will be adjusted. These changes will be submitted to the IRB as an amendment.

Study population and Recruitment:

Protocol #

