A new group of intensivists, oncologists, emergency medicine physicians and hospitalists will be recruited including resident and fellow trainees in those specialties. Physician subjects will be recruited face-to-face by the PI, through departmental email blasts and emails to contacts of the study team. As in phase 1, physicians will complete a screening questionnaire to exclude those that do not routinely encounter hospitalized patients with a life expectancy of less than one year. Potential subjects will be asked about the frequency and timing of previous communication and bias training. Physicians practicing Hospice and Palliative Medicine will be excluded because of their extensive prior training in communication.

Data collection:

Encounters will be videotaped. We will use the five-point verbal communication rating scale and nonverbal communication behaviors coded with the NAAS during the standardized encounter as described in phase 1 above.^{111,114} A research assistant who did not participate in the training sessions and is blinded to participant group will code communication behaviors. Subjects will complete the IAT and the questionnaire described in phase 1 immediately after the first encounter.

Outcome measures:

Subjects will complete an on-line questionnaire at the close of the session with Likert-type questions on the usefulness and acceptability of the training program and self-efficacy with cross-cultural communication. In addition, the questionnaire will include the cognitive and affective empathy portions of the Interpersonal Reactivity Index. For participants in the active group only, several questions will assess the illusion of ownership of the virtual body in the VR experience. An open-ended text box will invite feedback. The primary efficacy endpoint will be verbal dominance (ratio of clinician to patient speaking time during the encounter with a ratio of >1 meaning that the clinician dominated the discussion).⁹⁹ Secondary endpoints will include

Protocol #

verbal and nonverbal communication and encounter duration. Inter-rater reliability for the communication scores will be reported using Kappa values.

Analysis plan:

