Potential risks: This research poses two main risks to subjects: 1) emotional distress and 2) risk to privacy. There may be some emotional distress caused by learning about one's unconscious racial biases. Emotional distress may also result from passive deception; subjects will not be told that racial bias is the focus of the study until after the intervention. Privacy risk arises because racial biases may be considered sensitive information about the subject.

Adequacy of Protection Against Risks

Recruitment and Informed Consent: All subjects will be recruited by the PI through departmental email blasts, emails to contacts of the study team and departmental faculty meeting presentations. The consent process will take place in the Clinical Skills Center on the prior to the standardized patient encounter. Subjects will be informed of their right to participate or discontinue participation at any time without jeopardizing their employment, professional position or relationships with colleagues. Copies of the signed consent form will be given to the subject and placed in the subject's research folder in a locked file drawer in an office in the PI's office expressly designed for this purpose.

Incomplete disclosure of information during the consenting process: Subjects will be informed that they are participating in a study exploring physician cognition, cognitive biases and communication behavior. They will be informed that study participation includes completion

Protocol #

of an on-line instrument after the standardized patient encounter. They will not be told during the consent process that implicit racial bias and stereotyping are the focus of the study.

Incentives: Incentives have been chosen to provide a counterbalance to the opportunity costs of participating by offering continuing medical education (CME) credits for attending physician participants. Given that CME credits can be obtained in many ways, this incentive is not to be enough to be coercive. Since resident and fellow participants are unable to use CME credits during training, they will be offered a \$50 gift card to compensate them for their time.

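### The Phase 2 envelope may be opened as soon as consent is given, so the arm can be known before the baseline encounter and IAT are measured

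*Combined protocol and SAP*

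**What the plan says.** The timing has to be pieced together from several sections of the combined protocol and SAP.

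- **Phase 2, Design.** The trigger for allocation is "After a subject has been enrolled into the study and consented, the next sequence numbered envelope on the stack will be opened". No other time point is given. The active-arm slip begins "Intervention (Communication + Bias"; the control slip mentions communication only. The PI is named as executor and a research assistant as allocator.
- **Recruitment and Informed Consent.** "The consent process will take place in the Clinical Skills Center on the prior to the standardized patient encounter". A word is missing, but consent clearly precedes the encounter.
- **Phase 2, Design.** Simulations are recorded "before and after receiving the intervention or control", and "The intervention and simulations will take place in one half-day workshop".
- **Phase 2, Data collection.** "Subjects will complete the IAT and the questionnaire described in phase 1 immediately after the first encounter". The research assistant who codes the videos is blinded to group. Nobody else is stated to be.
- **Phase 2, Analysis plan.** The model for the post-intervention score has "pre-intervention score and intervention arm as the main effects". An IAT-by-arm interaction is added to test effect modification.
- **Risks/Benefits.** "subjects will not be told that racial bias is the focus of the study until after the intervention". The Debriefing paragraph instead puts full disclosure after the on-line bias instrument. The two differ, but both mean participants to be unaware of the racial focus throughout the first encounter and the IAT.

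**The concern.** A baseline covariate and an effect modifier should be fixed before anyone who could influence them knows the arm. Here both are behavioural. The first-encounter score depends on how the physician behaves and, for the speaking-time ratio that is the primary endpoint, on how the standardized caregiver behaves too. The IAT is taken straight afterwards. If the arm is known to either person by then, the baseline can differ by arm for a reason other than chance. Adjusting for it then adds bias instead of removing noise.

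The protocol takes this route seriously itself. Its section on the necessity of withholding information argues that knowing the study's intent would probably change how physicians communicate and so invalidate the results. Allocation concealment, which the Design section does provide, protects enrolment. It does not protect measurements made after the envelope is opened. Blinding the coder protects the scoring of the video, not the behaviour recorded on it.

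**Working it through.** **1. Order of events.** Fixed by the text: consent precedes the first encounter; the IAT and questionnaire follow the first encounter immediately; training comes between the two encounters. For the envelope, only a lower bound is fixed: after enrolment and consent. Two sequences satisfy every sentence:

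- consent, envelope, first encounter, IAT, training;
- consent, first encounter, IAT, envelope, training.

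The first is the natural reading, because consent is the only trigger named. Nothing rules it out.

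**2. The plan's own figure.** The Analysis plan states 80% power for an effect size of 0.8 with 25 per arm and a two-sided 5% level. Normal approximation: 0.8 × √(25/2) = 2.83; 2.83 − 1.96 = 0.87; power 80.7%. The noncentral t gives 79.1%. The figure reproduces and does not depend on when the envelope is opened.

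**3. What a baseline shift would do.** The documents give neither a shift nor a pre-post correlation, so both are assumed. Let s be the shift in the active arm's baseline (in SD, positive meaning better communication) and ρ the pre-post correlation. There is no true effect.

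If the shift has gone by the second encounter:

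- bias of the adjusted model ≈ −ρ × s
- bias of the change score ≈ −s

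Results from 20,000 simulated trials per row, 25 per arm. The change score is a simple contrast between arms, without the IAT terms.

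| s | ρ | Adjusted bias | Adjusted type I error | Change-score bias | Change-score type I error |
|---|---|---|---|---|---|
| 0 | 0.3 / 0.5 / 0.7 | about 0 | 5.0 / 4.9 / 5.2% | about 0 | 4.8 / 5.1 / 5.1% |
| 0.2 | 0.3 | −0.06 | 5.4% | −0.20 | 9.0% |
| 0.2 | 0.5 | −0.10 | 6.6% | −0.20 | 10.6% |
| 0.2 | 0.7 | −0.14 | 10.2% | −0.20 | 14.6% |
| 0.5 | 0.3 | −0.15 | 8.3% | −0.50 | 30.9% |
| 0.5 | 0.5 | −0.25 | 16.0% | −0.50 | 40.8% |
| 0.5 | 0.7 | −0.35 | 36.8% | −0.50 | 60.5% |

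If the shift persists equally at both encounters, the change-score bias is s − s = 0. The adjusted bias becomes s − ρs = (1 − ρ) × s, with the opposite sign: from 0.3 × 0.2 = +0.06 to 0.7 × 0.5 = +0.35 SD.

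**4. The interaction.** In the displayed change-score equation, a constant shift δ in the active arm's IAT moves the arm coefficient by −(β1 + β2) × δ and leaves β2 alone. β2 itself is distorted if the response to knowing the arm varies with the level of bias, which is the very pattern the interaction is meant to detect.

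**The case against.** Three stronger readings are tempting, and the documents support none of them.

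- **The plan states that the arm is revealed before baseline.** It does not. The trigger sets an earliest time only, and opening the envelope after the IAT would also comply. What stands is that the text permits the earlier opening, most naturally suggests it, and contains no safeguard against it.
- **Participants learn their arm, and the slip tells them what consent withheld.** Nothing says that participants or caregivers see the slip, and the Risks/Benefits section intends participants to stay unaware of the racial focus. The slip says bias, not racial bias, and the consent information already mentions cognitive biases in both arms. The cue may therefore be weak. It is still attached to one arm only.
- **The false-positive rate rises to about 40% in favour of the intervention.** The largest adjusted figure, 36.8%, takes both assumptions at their extreme. If the cue improves baseline behaviour and then fades, the excess rejections go against the intervention and a real benefit is understated. At ρ = 0.5 and a true effect of 0.8, the change-score effect falls to 0.8 − 0.2 = 0.6 or 0.8 − 0.5 = 0.3, and power from 79% to about 54% or 18%. If the cue persists, the sign of the adjusted bias reverses.

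It is also fair to say that randomizing after consent with numbered opaque envelopes is conventional, that this is a pilot aimed mainly at feasibility, and that everything fits into one half-day. These points limit the likely harm. They do not supply the missing rule.

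**Conclusion.** The point holds as a weakness in sequence. As written, the arm can be, and on the natural reading is, revealed at least to the PI before the measures used as baseline covariate and effect modifier are taken. Blinding is stated for the coder alone.

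Whether this would bias anything depends on facts the documents do not give: who sees the slip, whether it changes behaviour, and whether any change lasts to the second encounter. The tabulated biases and error rates illustrate assumed shifts and correlations; they are not estimates for this trial. A later opening time is worth adopting because it closes the route whatever those facts are, and the protocol's own reason for withholding its focus argues for closing it. Label: cheap improvement.

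**What to change.** In Phase 2, Design, replace the trigger for opening the envelope along these lines: *The next numbered envelope is opened only after the participant has completed the first encounter, the IAT and the questionnaire, immediately before training begins.* In addition:

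- replace the wording on the slip with a neutral code (A or B);
- state who learns the arm and when, and keep the standardized caregivers unaware of it at both encounters;
- reconcile the two statements of when the racial focus is disclosed (after the intervention, or after the bias instrument), so that the masking period is unambiguous.

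Cost: a few sentences. Sample size and planned power are unchanged (25 per arm; 80.7% by normal approximation, 79.1% by t). The one practical burden is that both sessions must be ready to run once baseline ends, and the small groups for the VR debriefing can be formed only then. Baseline and training already share one half-day workshop, so the delay is short. If it cannot be scheduled, the allocator can hold the result unseen by participant, PI and caregivers until the baseline measures are complete.
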